2.6 P95 Research Team

4 PROTOCOL SUMMARY

Title of study:

Pilot study to assess detection of RSV, hMPV and PIV when using multi-specimen collection compared to a single nasopharyngeal swab

Background and rationale:

Severe respiratory viral infections pose a significant health burden among adults, leading to substantial morbidity and mortality. Most incidence estimates are based on real-time polymerase chain reaction (RT-PCR) testing of nasopharyngeal swabs. However, the recent North American Multispecimen Study showed a several-fold increase in respiratory syncytial virus (RSV) diagnosis in adults when additional specimen types were added to nasopharyngeal swabs. This study as well as others demonstrate that the true RSV disease burden is underestimated in nasopharyngeal only studies [1-4].

With this study, we aim to gain insights into the possible underestimation RSV, human metapneumovirus (hMPV) and parainfluenza virus (PIV) detection rates in patients with an (severe) acute respiratory infection ((s)ARI) by using additional specimen types (oropharyngeal swabs, saliva, sputum and blood samples) and compare to the results by nasopharyngeal swabs only.

Objectives:*Primary objective:*

1. To assess the detection rates (%) of RSV, hMPV and PIV in adult (s)ARI patients (≥ 18 years), when using multi-specimen collection compared to a single nasopharyngeal swab, overall and by additional specimen type.

Secondary objectives:

2. As primary objective, stratified by
 - Age categories: 18-49, 50-59, 60-74, 75+
 - Sex at birth
 - Time since symptom-onset categories
 - By setting (hospital, emergency department (ED) ward and primary care center (PCC))
 - By diagnosis (upper respiratory tract infection vs. lower respiratory tract infection and pneumonia, bronchitis, bronchiolitis, etc.)
 - By common comorbidities/ chronic conditions
3. As primary objective, stratified by
 - Vaccination status
 - RSV detection rates by RSV vaccination status (ever vaccinated or unvaccinated)
4. To assess the detection rates (%) of SARS-CoV-2 and Influenza in adult (s)ARI patients (≥ 18 years), when using multi-specimen collection compared to a single nasopharyngeal swab (overall and by additional specimen type), overall and stratified by:
 - SARS-CoV-2 detection rates (%) by SARS-CoV-2 vaccination status (vaccinated in the last 12 months or not vaccinated in the last 12 months)
 - Influenza detection rates (%) by Influenza vaccination status (vaccinated in the last 12 months or not vaccinated in the last 12 months).

Exploratory objectives:

5. To assess the detection rates (%) of co-infections (all pathogens tested) in adult (s)ARI patients (≥ 18 years), when using multi-specimen collection compared to a single nasopharyngeal swab, overall and by additional specimen type.
 - And stratify by disease severity (PCC, ED ward, hospitalization, death), if the sample size allows.
6. As primary objective, stratified by subtype or serotype (when applicable)
 - RSV detection rates by RSV subtype A and B
 - PIV detection rates by PIV serotype (1-4)
7. To assess the detection rates (%) of Influenza, SARS-CoV-2 and other viral pathogens tested for with the RT-PCR multiplex panel in adult (s)ARI patients (≥ 18 years), when using multi-specimen collection compared to a single nasopharyngeal swab, overall and by additional specimen type.

Study design:

Multi-setting (inpatient, ED ward and PCC) prospective cohort study of (s)ARI cases

Study duration:

Recruitment period: 7th of January 2026 – 30th of June 2026. Sample collection between 7th of January 2026 and 31st of July 2026.

Inpatient setting: baseline samples to be taken within 48 hours of hospital admission, as soon as possible after admission. Convalescent blood sample to be taken between 25 and 31 days after hospital admission.

ED and PCC setting: baseline samples to be taken within the initial consult.

Population, setting and eligibility criteria:**Study setting:**

A pilot study will be conducted in one (1) hospital ([name], Valencia), one (1) ED ward ([name], Valencia), and up to four (4) PCC, all based in Valencia, Spain.

Study participants: Patients are included if they are:

- Adults aged 18 years and older
- AND
- Meet the (s)ARI case definition
- AND
- Willing to have a nasopharyngeal and oropharyngeal swab collected as well as saliva. Sputum and serology are optional and will be consented for on the informed consent form (ICF) as separate items.
- AND
- Willing and able to provide informed consent, obtained from the patient or from the patient's Legally Acceptable Representative(s).

Individuals (patient) cannot be enrolled if:

- patient cannot be swabbed due to severe septum deviation, obstruction, or other conditions that contra-indicate swabbing,
- patient was previously enrolled in the study within 30 days of their current visit/admission,

- patient develops signs and symptoms of (s)ARI after being hospitalized.

(s)ARI case definition:

A (s)ARI case is defined as a patient with a suspicion of a respiratory infection with at least one of the following symptoms:

- cough
- fever (≥ 38 C°)
- shortness of breath
- sudden onset of anosmia, ageusia, or dysgeusia

with symptom onset within the last 14 days prior to hospital admission and symptoms occurring for at least 24 hours.

Patient recruitment:

In the hospital setting, (s)ARI patients will be recruited between Monday and Friday. Patients submitted during the weekend will be enrolled on Monday if sample collection can be performed within the allowed time frame. During January and February a maximum of 100 patients per month will be consecutively recruited during the week (Monday to Friday). Recruitment will be halted after 100 patients are recruited. During the other months with expected high hMPV and PIV circulation, all (s)ARI patients will be approached.

For both the ED ward and PCC setting, (s)ARI patients will be recruited consecutively during the week (Monday to Friday). Each week 12 (s)ARI patients will be recruited from each setting. During the peak season of respiratory illnesses, the targets will be reached before Friday after which recruitment will be halted for that week. In slower recruitment weeks, all patients will need to be approached to reach the target sample size of 12 (s)ARI patients.

Planned study recruitment period:

7 January 2026 – 30 June 2026

Last patient in on 30 June 2026, last sample taken by the 31st of July 2026.

Laboratory testing:

The following clinical specimens will be collected from all recruited patients during the study period:

Hospital setting:

At baseline: (as soon as possible, within 48 hours of hospital admission):

- 1x nasopharyngeal
- 1x oropharyngeal swab
- 1x Saliva
- Optional: 1x Sputum sample
- Optional: 1x Blood sample

At convalescence (28 days (+/- 3 days) after hospital admission)

- 1x Blood sample (if a baseline sample was taken)

ED ward and PCC

At baseline: (within the original of visit)

- 1x nasopharyngeal swab
- 1x oropharyngeal swab
- 1x Saliva
- Optional: 1x Sputum sample

Respiratory samples:

All respiratory samples (nasopharyngeal, oropharyngeal, saliva, and sputum samples) will be tested for RSV A and B, PIV serotypes 1-4, and hMPV, by using a commercial RT-PCR kit, which also tests for presence of SARS-CoV-2, Influenza A, Influenza B among others. Study Contributor will be requested to submit validation logs (summarizing the quality check process, results, timing and certificates of analysis for assays performed).

Blood samples:

Acute and convalescent paired blood specimens will be collected for serological testing for RSV A and B, hMPV and PIV 1-4. Blood samples will be centrifuged to separate the serum, which will be stored at -20°C until shipment to the central laboratory in Lyon for testing. Enzyme-Linked Immunosorbent Assay (ELISA) technique will be used to detect and quantify IgG antibody titers. Serology will be considered positive for a recent infection when a 4-fold or greater rise in virus specific IgG antibodies is found between the paired acute and convalescent blood samples.

The laboratory in Lyon will deliver the following variables:

- RSV-A IgG antibody titers baseline
- RSV-A IgG antibody titers convalescence
- RSV-B IgG antibody titers baseline
- RSV-B IgG antibody titers convalescence
- hMPV-A IgG antibody titers baseline
- hMPV-A IgG antibody titers convalescence
- hMPV-B IgG antibody titers baseline
- hMPV-B IgG antibody titers convalescence
- PIV1 IgG antibody titers baseline
- PIV1 IgG antibody titers convalescence
- PIV2 IgG antibody titers baseline
- PIV2 IgG antibody titers convalescence
- PIV3 IgG antibody titers baseline
- PIV3 IgG antibody titers convalescence
- PIV4 IgG antibody titers baseline
- PIV4 IgG antibody titers convalescence

Storage:

To support potential future analyses and ensure the integrity and reproducibility of study findings, multiple biological samples per participant will be collected and aliquots will be stored under controlled conditions for long-term preservation when there is specimen left over.

Variables:

At baseline, information on covariates will be collected from patients in all settings through an electronic Case Report Form (eCRF). Set-up and questions will be based on the eCRF used for the id.DRIVE surveillance project. The following variables will be collected:

- Age
- Sex at birth
- Setting id
- Diagnosis (upper respiratory tract infection or lower respiratory tract infection)
- Admitting diagnosis (Pneumonia, Bronchitis, Bronchiolitis)
- Chronic conditions/ Comorbidities:
 - o chronic lung disease
 - o chronic cardiovascular disease
 - o hypertension
 - o chronic liver disease
 - o chronic renal disease
 - o type 1 and type 2 diabetes
 - o cancer
 - o immunodeficiency disorders
 - o obesity
 - o neurological disorders
- Immunodeficiency (e.g., on immunosuppressants)
- Long-term care facility residence
- Vaccination status (RSV, Influenza, SARS-CoV-2), including date of last vaccination
- Specimen test results, specimen type, date of sampling
- Symptoms
- Date of symptom-onset

Data sources:

After study enrolment, data will be collected from primary (e.g., laboratory results) and secondary data sources (e.g., vaccination registries, medical files).

Exposure status, brand information and date of vaccination(s) will be ascertained by consulting vaccination registries. Where needed, treating physician or other health care professionals will be contacted to obtain additional information.

Study size:

Target sample size: 1074 (s)ARI patients (450 in hospital; 624 in PCC and ED):

Data analysis:

The rate of respiratory pathogen diagnosis from nasopharyngeal swab alone will be determined by dividing the count of patients in which the respiratory pathogen of interest was detected solely by nasopharyngeal swab by the total patient count involved in this study, thereby yielding detection rates. The same calculation will be performed for the other specimens, oropharyngeal swab, saliva, blood, and sputum, as well as the detection rates when different specimen types are combined. We will determine the increase in detection rates for each specimen added, using nasopharyngeal only as a reference point. Results will also be presented for different subgroups to explain potential heterogeneity. All included patients are required to have at least a nasopharyngeal swab, oropharyngeal swab and a saliva sample. Euler diagrams will be employed to illustrate respiratory pathogen diagnosis per specimen type. The sensitivity for each specimen type and combination thereof will also be computed.

Data management:

Data collected at Study Contributors will be checked for quality and transferred to a dedicated, secured central server hosted by P95. A data management plan (DMP) will be written prior to the start of the data collection. The DMP will describe all functions, processes, responsibilities and specifications for data collection, cleaning, and validation.

Quality control:

Within the data analysis workflow and quality control process, one statistician will develop the R code, and a second statistician will review it to confirm accuracy, reproducibility, and compliance with coding standards. Following the coding QC, the results are reviewed by epidemiologists to assess their validity, interpretability, and relevance in the context of the study's design and public health implications.

Limitations of the research methods:

- Limited samples size, especially as some pathogen (subtypes) are rarely detected.
- RT-PCR offer high specificity. However, a positive RT-PCR result may not indicate causality for (s)ARI (persistent nucleic acid from previous infection, or asymptomatic carriage).
- Despite good sensitivity and specificity of the selected serology assays, false-negative (e.g., immunodeficiency disorder) and false-positive (e.g., cross-reactivity) test results are possible.
- The second blood sample will be collected approximately four weeks after hospital admission when the majority of patients will be home again. A nurse will be hired to follow-up with patients at home or patients will be provided with transportation costs to increase the likelihood of getting all required samples, however there still might be patients that are lost to follow-up.
- Viral load is variable and usually decreased over time. Delays between symptom onset and sample collection could affect detection rates and diagnostic accuracy.

References:

1. C. Onwuchekwa et al. (2023) Underascertainment of Respiratory Syncytial Virus Infection in Adults Due to Diagnostic Testing Limitations: A Systematic Literature Review and Meta-analysis. *J Infect Dis.* 228(2):173-184. doi: 10.1093/infdis/jiad012.
2. E. Begier et al. (2025) Detection of RSV using nasopharyngeal swabs alone underestimates RSV-related hospitalization incidence in adults: the Multispecimen study's Final Analysis. Preprint. <https://doi.org/10.1101/2025.01.14.25320406>
3. Y. Li et al. (2023) Adjusting for Case Under-Ascertainment in Estimating RSV Hospitalisation Burden of Older Adults in High-Income Countries: a Systematic Review and Modelling Study. *Infect Dis Ther.* 12(4):1137-1149. doi: 10.1007/s40121-023-00792-3
4. Zhang et al. (2016) Serology Enhances Molecular Diagnosis of Respiratory Virus Infections Other than Influenza in Children and Adults Hospitalized with Community-Acquired Pneumonia. *J Clin Microbiol.* 55(1):79-89. DOI: 10.1128/JCM.01701-16

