12.9.1 Sample Size Considerations

Sample size were calculated assuming paired designs across various scenarios, assuming the addition of one extra specimen per patient and the simplifying assumption that all positives by Method A are also positive by Method B (i.e., the gain equals the proportion A-/B+). These calculations were based on pathogen incidence rates ranging from 1% to 10% and varying levels of improved detection with an additional sample. Across all settings, we expect data from over 1,000 patients with at least two specimens available (approximately 450 inpatients and 624 outpatients).

Under these assumptions, with the planned combined samples ($N \approx 1,074$), we have adequate precision to assess a doubling of detection rates — consistent with the Pfizer North America Multispecimen Study [6] — for pathogens with an incidence between 1% -7% range. For such doublings, the 95% confidence intervals on the gain are expected to be approximately ± 0.6 and ± 1.8 percentage points overall (interval with ≈ 1.2 —3.6 pp), depending on the baseline incidence.

While analyses stratified by settings will be possible, they will have wider confidence intervals due to smaller sample sizes.

The analysis of the 150 patients with available serology data will be exploratory, with limited statistical power, as we expect only a small number of PIV and/or hMPV cases in this subgroup.

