12.9.3 Data Analysis

12.9.3.1 Detection rates of respiratory pathogens

Positive laboratory results for each respiratory pathogen of interest will be reported by specimen type. This includes nasopharyngeal swabs, saliva, blood, and sputum. Serology is considered positive for recent infection if a fourfold or greater rise in virus-specific IgG antibodies is observed between paired samples. If all samples (respiratory and blood samples) collected in the time frame are negative, the patient is considered as not having any laboratory-confirmed infection.

For each specimen type, the percentage of positive diagnoses will be calculated by dividing the number of patients in whom the pathogen was detected using that specimen (alone or in combination) by the total number of included patients. Detection rates in sputum and blood samples will be calculated by dividing the number of patients in whom the pathogen was detected using that specimen (alone or in combination) by the total number of included patients who provided sputum or blood samples.

Comparative detection rates will be assessed by calculating the percentage increase in positivity when additional specimen types are included, using nasopharyngeal as the reference. This will allow evaluation of the incremental diagnostic value of each specimen type.

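### The protocol summary and Section 12.9.3.1 give different numerators for the nasopharyngeal reference rate; read literally, the summary's rule overstates the gain from added specimens

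*Protocol*

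**What the plan says.** The primary objective (Section 11.1) compares detection of RSV, hMPV and PIV by multi-specimen collection with detection by a single NP swab. The NP rate is the reference for that comparison, and the protocol defines it twice.

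- **Protocol Summary, Data analysis.** The NP rate comes from "dividing the count of patients in which the respiratory pathogen of interest was detected solely by nasopharyngeal swab by the total patient count". The summary continues: "The same calculation will be performed for the other specimens, oropharyngeal swab, saliva, blood, and sputum". The gain follows: "We will determine the increase in detection rates for each specimen added, using nasopharyngeal only as a reference point".
- **Section 12.9.3.1.** The rate for each specimen comes from "dividing the number of patients in whom the pathogen was detected using that specimen (alone or in combination) by the total number of included patients". For sputum and blood the division is "by the total number of included patients who provided sputum or blood samples". The comparison is made by "calculating the percentage increase in positivity when additional specimen types are included, using nasopharyngeal as the reference".

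Section 12.9.1 sizes the study on a doubling of detection, with the gain defined as the proportion negative by Method A and positive by Method B. Every Method A positive therefore belongs to the reference, which agrees with 12.9.3.1.

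**The concern.** A count of patients in whom a virus was found *solely* by one specimen ordinarily means that no other specimen found it. That is the NP-exclusive region of the planned Euler diagram. It is not what a single NP swab detects: a clinician using one swab finds every NP-positive patient, whatever saliva or sputum would have shown.

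Under the literal summary rule, a patient positive on both NP and saliva leaves the reference but stays in the multi-specimen total, and so is counted as gain from the extra specimens. The error runs in one direction only: NP swabs look less sensitive than they are. Under-ascertainment by NP swabs is the question the study is meant to answer, and an interim report is due after three months of data collection.

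The denominators also differ. The summary uses the total patient count for every specimen, including optional sputum and blood, while 12.9.3.1 restricts those two to patients who provided them.

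**Working it through.** **Inputs.** From the protocol: N = 450 + 624 = 1,074; planned effect a doubling; baseline incidence 1% to 7% (Section 12.9.1). Assumed: s, the share of NP positives also positive on at least one other specimen. The protocol gives no figure for it, so it is varied over its whole range.

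**The plan's own figures.** With all NP positives in the reference, the gain g has 95% half-width 1.96 × √(g(1-g)/1,074). At g = 1% this is 0.595 percentage points, matching the stated ±0.6. At g = 7% it is 1.53, not the stated ±1.8; g = 10% gives 1.79. That mismatch is a separate matter and does not affect this point. The lower figure confirms that the precision calculation works on a paired gain.

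**Effect of the literal rule.** Let p be the true NP rate and 2p the combined rate.

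- Section 12.9.3.1: reference p; relative increase (2p - p)/p = 100%; absolute gain p.
- Summary, read literally: reference p(1-s); relative increase (2p - p(1-s))/(p(1-s)) = (1+s)/(1-s); absolute gain 2p - p(1-s) = p(1+s).

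| s (assumed) | Reference count, p = 1% | Reference count, p = 7% | Relative increase | Gain, p = 1% (pp) | Gain, p = 7% (pp) |
|---|---|---|---|---|---|
| 0 | 10.7 | 75.2 | +100% | 1.00 | 7.00 |
| 0.10 | 9.7 | 67.7 | +122% | 1.10 | 7.70 |
| 0.25 | 8.1 | 56.4 | +167% | 1.25 | 8.75 |
| 0.50 | 5.4 | 37.6 | +300% | 1.50 | 10.50 |
| 0.70 | 3.2 | 22.6 | +567% | 1.70 | 11.90 |
| 1 | 0 | 0 | undefined | 2.00 | 14.00 |

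The first row is also the correct answer under 12.9.3.1 for any s.

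**Against the stated precision.** The error in the absolute gain is p × s. At p = 7% and s = 0.25 it is 1.75 percentage points, about the stated half-width of 1.8. At p = 1% and s = 0.50 it is 0.50, just below the stated 0.6. The relative measure is much more sensitive.

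**Denominator for blood.** Section 12.9.1 expects about 150 patients with serology. Dividing the same positives by 1,074 rather than 150 changes the blood rate by a factor of 1,074/150 = 7.2. This conflict does not depend on how *solely* is read.

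**The case against.** The strongest reply is that *solely by nasopharyngeal swab* means judged on the NP result alone, with other specimens ignored. Much supports this. The same sentence introduces the quantity as the rate from an NP swab alone, and the Background uses similar words for a testing strategy. The summary goes on to combined specimens and to the increase for each specimen added; an NP-exclusive count would shrink as specimens were added and could not be a fixed reference. The summary also promises the sensitivity of each specimen type, which needs all its positives. On this reading there is no bias, only loose wording.

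It can be added that 12.9.3.1 is the detailed methods section and already holds the workable rule, and that the percentage increase is specified there, next to the correct numerator. The larger figures above arise only if the summary's literal numerator is put into that measure.

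Most of this stands, and it limits how firmly a bias can be asserted. It does not remove the contradiction. The literal meaning of the summary sentence is the opposite of alone or in combination, and the Euler diagrams will produce an NP-only region to which the word fits exactly.

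A reader might go further and infer that the summary's rule discards most NP positives and inflates the gain several-fold. The protocol does not support that. Discarding most requires s above 0.50, and no overlap is given. At s = 0.10 to 0.25 the relative increase is inflated only 1.2- to 1.7-fold. Nor does the sample-size assumption that all Method A positives are also Method B positives settle s. If Method B is the added specimen, it implies s = 1; if it is the combination, it is true by definition and says nothing about s.

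**Conclusion.** The point holds as a contradiction in the definition of the primary objective's reference rate, with a possible one-directional bias. If the summary is followed literally, any overlap between NP and other specimens overstates the gain: the relative increase for a true doubling rises from +100% to (1+s)/(1-s), and the percentage-point gain is multiplied by 1+s, never more than 2-fold. These sizes rest on the planned doubling and on an assumed s. Whether any bias occurs depends on which reading the analyst takes. Section 12.9.3.1, the wording of the objective and the sample-size basis all point to counting every NP positive. The denominator conflict for sputum and blood is a plain mismatch between the two sections.

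**What to change.** Replace the summary sentence with the 12.9.3.1 rule:

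- **NP rate:** all patients with a positive NP swab, whatever their other results, divided by all included patients.
- **Oropharyngeal swab and saliva:** the same rule, with that specimen's positives.
- **Sputum and blood:** positives on that specimen divided by the included patients who provided it.

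If patients positive on NP only are of interest, for example for the Euler diagrams, report them as a separately named count and do not use them as the reference for the gain.

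The cost is a sentence or two in the summary. Sampling, sample size and Section 12.9.3.1 need no change. The edit should be in place before the interim report is programmed.
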